New patients coming to see a specialist in the Arthroplasty group at MGH complete surveys in the clinic via a computer or tablet. The surveys cover quality of life, pain, functioning and symptoms and are administered through the Harris Joint Registry (IRB # 2002-P-001823). The surveys for this study will be incorporated as an additional module in the Harris joint registry for arthroplasty patients at MGH and will be administered by paper, by computer in the clinic or via Redcap depending on the patients' preference and the timing of the visit. The new patients at NWH will similarly be offered to complete the patient reported quality and functional status surveys by paper, by computer or tablet in the clinic, or by email in advance of their visit as covered by their patient reported outcome registry protocol (IRB protocol 2014P000696). New patients at NEBH will be asked to complete the quality of life surveys as part of the initial pre-visit survey for the study.

Briefly describe study procedures. Include any local site restrictions, for example, "Subjects enrolled at Partners will not participate in the pharmacokinetic portion of the study." Describe study endpoints.

Study Procedures:

1. The principal investigator will obtain permission from participating clinicians at each site to screen their patients for eligibility and enroll eligible patients onto the study. Some, but not all, participating clinicians may also be co-investigators.
2. The statistician will generate a random allocation sequence to indicate which decision aid each participant should receive. The statistician will also group providers at each site by patient

volume and randomly assign each group to the usual care or intervention group for the in visit intervention.

3. The research coordinator, with support from the research nurse or other clinic staff, will review the schedules of participating clinicians and the Epic research report, if available, to complete the eligibility screener to the extent possible and identify potentially eligible participants

4. The research coordinator may call potentially eligible patients to clarify any information about eligibility.

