14. About 6 months from the date of their initial visit, study staff will confirm participant surgical status and will send participants the third survey (T3) by mail or email. Non-surgical patients will receive T3 about 6 months from their consultation and surgical patients will receive T3 about 6 months from their surgery date. Study staff will follow up with a phone reminder within 1 week, a second mailing or up to three reminder emails as appropriate, and a second phone reminder for non-responders. For those who do not respond to the email reminders, we will mail them a survey before the second phone reminder.

15. All patients who receive the final survey will also be able to indicate their consent to be contacted in the future for other studies run out of the Health Decision Sciences Center. Of those patients who've given consent to be re-contacted: study staff may contact these patients via email or telephone, depending on their preferred method indicated, to invite them to participate in future projects and studies.

16. Study staff will review completed surveys soon after receipt and enter survey data into the study database as needed. If there are large portions of the surveys that are missing the study coordinator will contact the participant to determine whether the items were intentionally skipped

(in which case no further action will be taken) or whether it was not intentional and in this case will provide any needed clarification and request that the items be completed.

17. All participants who complete the T3 survey will receive a thank you note including an answer key to the knowledge section of the T1 and T2 surveys.

18. Study staff will collect additional data from the medical record (including patient demographics, treatments received for the hip/knee, co-morbidities, and clinician visits related to the hip/knee) in the 12 months since the initial visit, patient-reported quality of life and functional status data from the Harris Joint Registry and Newton Wellesley Hospital's Kaplan Joint Center registry (IRB# 2014P000696) databases, and use of decision aids from the Shared Decision Making database (IRB 2005p-002282).

19. Limited data will be kept on non-responders including joint, age, gender, physician, decision aid assignment, reason for refusal (if available), and all elements in the eligibility screener. This information will be used to examine non-response bias.

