3. Functional goals (T2, T3): participants will list the top three things that they need or want to do but are unable to do because of their knee or hip pain (at T2). Then at T3, they will indicate to what extent they are able to do those three things.

- 4. SURE scale (T2):** A brief, 4-item version of the widely used Decisional Conflict Scale (15) that measures patients' uncertainty about which treatment to choose and factors contributing to uncertainty (feeling uninformed, unclear values, and unsupported in decision making).
- 5. Decision regret (T3):** 5-item Likert scale that measures distress or remorse after a decision. A total score (0-100) is calculated with higher scores indicating more regret. The scale has demonstrated strong internal consistency (0.81-0.92) and correlates with decision satisfaction and quality of life (16).

Health Outcomes Measures (timing of use)

- 6. EQ-5D (T1, T3)** is a 6-item summary measure of health status for use in evaluating health and healthcare (17). It also generates a single index value for health status on which full health is assigned a value of 1 and death a value of 0. In conjunction with weights established for the 243 different combinations, the EQ-5D can be used to obtain quality-adjusted life years (18). The minimally important change is 0.1 points (19).
- 7. Knee injury and osteoarthritis score (KOOS) (T1, T3)** The KOOS and HOOS questionnaires were developed to assess the patients' opinions about their knee or hip and associated problems and have been used extensively (20-28). Three subscales, pain, symptoms and functional status will be used in this study. A normalized score (100 indicating no pain/symptoms and 0 indicating extreme pain/symptoms) is calculated for each subscale.
- 8. Harris Hip Score (HHS) (T1, T3):** The HHS assesses pain, function, range of motion and deformity for each hip. Pain receives 44 points, function 47 points, range of motion 5 points, and deformity 4 points for a total of 100 points. Function is subdivided into activities of daily living (14 points) and gait (33 points). The higher the HHS, the less dysfunction. A total score of 70 is considered a poor result; 70 – 80 is considered fair, 80 –90 is good, and 90 –100 is an excellent result. No normative values are available.

Additional items

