- 9. PDA use (T1, T2):** items will assess how much of the DVD, booklet and/or website was reviewed (all, some, a little, none) and how much time did they spend reviewing it (0-5 minutes; 6-10 minutes; 11-20 minutes; 21-30 minutes; >30 minutes).
- 10. Treatment received (T3, chart review):** surgical and non surgical treatments tried in the twelve months after the visit will be self reported by patients and also collected via chart review.
- 11. Expectations (T2, T3):** 4 items will assess expectations for pain relief, limitations in daily activities, overall success of surgery and complications (29).
- 12. Demographics (T2):** information such as education, employment, marital status will be self reported.
- 13. Satisfaction (T2, T3):** questions to assess overall satisfaction with quality of visit or treatment outcome
- 14. Information use (T3):** 1 question to assess what sources of information patient about their health condition they found important
- 15. IMPACT index (T2, T3):** 7 items assessing the impact of hip and knee osteoarthritis on patients' perception of their condition: worry, pain, limitation, confidence, and involvement in decision making.

Table 3: Measures including in surveys

Measures	Pre-visit (T1)	~ 1 week (T2)	~ Follow-up (T3)
Visit goals and functional goals	2 (physician intervention group only)		
		12	

Decision Quality Instrument	9		0
Decision aid use	1	1	Not asked
Decision making process	0	11	7
Functional goals	Not asked	2	1
SURE	Not asked	4	Not asked
Expectations	Not asked	10	10
Quality of life, pain and functioning (KOOS or HHS, EQ-5D)*	Routinely collected	Not asked	Routinely collected
Decision Regret	Not asked	Not asked	5
Satisfaction	Not asked	1	2
Demographics and treatment history		5	2
Health literacy	1	Not asked	Not asked
Impact Index	Not asked	7	7
Total number of items	13 (MD usual care group)/ 15 (MD intervention group)	53	34
Total time estimate	5 minutes	15 minutes	15 minutes

*These items are asked as part of routine care at this time point.

Randomization and blinding

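### No T3 route is given for EQ-5D and KOOS/HHS at New England Baptist Hospital, and no T3 fallback at any site, so Hypothesis 2.1 could lose one hospital's outcome data

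*Protocol*

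**What the plan says.** - **Protocol, Table 3.** The row "Quality of life, pain and functioning (KOOS or HHS, EQ-5D" is marked as routinely collected at T1 and T3 and not asked at T2. Its footnote reads "These items are asked as part of routine care at this time point". The T3 survey is stated to have 34 items and to take 15 minutes.
- **Protocol, Study Procedures, step 18.** Study staff will obtain "patient-reported quality of life and functional status data from the Harris Joint Registry and Newton Wellesley Hospital's Kaplan Joint Center registry". No NEBH source is named.
- **Protocol, Research Design and Methods.** MGH and NWH collect these scores around the first visit under their own registry protocols. The third site differs: "New patients at NEBH will be asked to complete the quality of life surveys as part of the initial pre-visit survey for the study".
- **Protocol, Study Procedures, step 11.** If the routine quality-of-life questionnaire was not completed at the visit, it goes out with the T2 survey.
- **Protocol, Study Procedures, step 14.** This step sets the T3 mailing and its reminders. For example, "Non-surgical patients will receive T3 about 6 months from their consultation", while surgical patients are timed from their operation. It does not mention adding quality-of-life or function items.
- **Protocol, Specific Aims.** Aim 2 concerns overall quality of life and functional status. Hypothesis 2.1 compares health outcomes between patients with high and low decision quality.
- **SAP, missing-data paragraph.** Item-specific primary analyses leave out patients with missing data. Last value carried forward, EM single imputation and multiple imputation are sensitivity analyses.

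**The concern.** EQ-5D and KOOS/HHS are the measures of the two outcomes that Aim 2 names. At T3 the study does not collect them itself but relies on routine care, and the named sources are the registries of two of the three hospitals. At NEBH the scores had to be built into the study's own survey at T1, which suggests that no equivalent routine collection exists there. If nobody adds them at T3, that hospital has baseline scores and no follow-up scores.

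The loss would follow site rather than chance. With no NEBH follow-up scores at all, nothing within the trial could show whether NEBH patients resemble those at the other two hospitals. Scores not collected when T3 is due cannot be recovered later.

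**Working it through.** **1. Does the T3 survey contain the scores?** Table 3, T3 column: Decision Quality Instrument 0, decision-making process 7, functional goals 1, expectations 10, regret 5, satisfaction 2, demographics and treatment 2, Impact Index 7.

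0 + 7 + 1 + 10 + 5 + 2 + 2 + 7 = 34.

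This reproduces the stated "Total number of items" for T3 with nothing from EQ-5D, KOOS or HHS. The T2 column also reproduces: 12 + 1 + 11 + 2 + 4 + 10 + 1 + 5 + 7 = 53.

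**2. Could NEBH scores arrive another way?**
- Steps 9 and 18 draw quality-of-life data from the MGH and NWH registries.
- The Protocol section on receiving data from outside Partners says NEBH sends eligibility screeners, chart-review information and scanned study surveys. It names no registry.
- The chart-review content in step 18 is demographics, treatments, comorbidities and clinician visits, not questionnaire scores.

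The study survey is therefore the only described channel that could carry NEBH scores at T3, and Table 3 leaves them out of it.

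**3. Is there a fallback?** Step 11 has one for scores missed at the first visit. Step 14 has none for T3, at any site.

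**4. How many patients?** The Protocol projects 716 T3 respondents. NEBH's share, s, is not given, so it is an assumption here. Patients lost = 716 × s. Standard-error factor = 1/√(1 − s), taking the loss as unrelated to decision quality, with variance and clustering unchanged.

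| Assumed s | Lost | Remaining | SE factor |
|---|---|---|---|
| 20% | 143 | 573 | 1/√0.80 = 1.118 |
| one third | 239 | 477 | 1/√0.667 = 1.225 |
| 50% | 358 | 358 | 1/√0.50 = 1.414 |

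**5. Is power the problem?** Detectable EQ-5D difference = (1.960 + 0.842) × SD × √[1/(np) + 1/(n(1 − p))], for 80% power at two-sided 0.05. Assumptions: SD 0.15 to 0.25; proportion with high decision quality p of 0.65 or 0.83 (the SAP's two planning rates for Hypothesis 1.1); no clustering.
- n = 716: from 0.033 (SD 0.15, p 0.65) to 0.070 (SD 0.25, p 0.83).
- n = 358: from 0.047 to 0.099.

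The Protocol gives 0.1 as the minimally important change in EQ-5D. Even at half the sample the detectable difference stays below it, so on these assumptions the main difficulty is the site-level gap, not power.

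**6. Would the sensitivity analyses repair it?** Last value carried forward would give each NEBH patient the T1 score, that is, no change. EM and multiple imputation would have to borrow follow-up from MGH and NWH and assume that it applies to NEBH, with no NEBH T3 scores to test this.

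**The case against.** The strongest reply is that Table 3 was written for the two registry sites. It marks these measures as routine at T1 as well, although NEBH collects them in the study survey. The T1 column gives them no item count either: its rows as extracted sum to 11 (13 with the worksheet items) against a stated 13 and 15, and that gap of 2 could not hold even the 6 items of EQ-5D. So the count of 34 cannot by itself prove that NEBH patients go unasked at T3. The Measures section also lists EQ-5D, KOOS and HHS at T1 and T3 with no site exception, and step 18 does not say that its list is exhaustive. This stands as evidence that collection from everyone was intended. It supplies no T3 route for NEBH, and it confirms that Table 3 needs correcting.

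Four stronger readings are tempting and should not be drawn.

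- **Non-surgical patients will be missing more often, which biases Hypothesis 2.1.** The registries are described as covering hip and knee osteoarthritis patients, not only those operated on, and the Privacy and Confidentiality section allows surveys to be emailed through them. The documents do not say what registry follow-up a patient without surgery receives. Differential loss is possible but not established.
- **The hip score is capped or distorted.** HHS includes "range of motion 5 points, and deformity 4 points for a total of 100 points", and those 9 points may need an examination. Routine care could provide one, and no rule scores unexamined items as zero. What can be said is that the source of these 9 points is not stated.
- **NEBH patients would have no T3 health information.** The T3 survey still carries the Impact Index and the functional-goals item. These touch on pain and limitation, although they do not replace EQ-5D or KOOS/HHS.
- **Hypothesis 2.1 is the main Aim 2 question.** The Protocol does not rank it above Hypothesis 2.2.

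**Conclusion.** The point holds as a gap in the data-collection plan: an outcome needed for Hypothesis 2.1 has no described T3 source at one of three hospitals, and no T3 safety net at any of them. It should be closed before T3 surveys go out.

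The size of the loss is unknown because NEBH's share is not given. The range of 143 to 358 patients, with standard errors 12% to 41% larger, depends entirely on the assumed 20% to 50%. Neither a direction nor a size of bias can be derived from the documents. The conclusion also assumes that staff follow the text literally. If NEBH was in practice meant to receive these items in the T3 survey, what remains is an error of documentation, and the same correction applies. The opening part of the SAP was not available for this check, so nothing is inferred from the absence of a power figure for Hypothesis 2.1.

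**What to change.** 1. Include EQ-5D and the self-report KOOS or hip items in the T3 survey at NEBH.
2. At MGH and NWH, include them for any patient without a registry score near the T3 date, with that window defined. Alternatively, include them for all patients at all sites and use registry values as back-up, which is simpler to run and gives one mode of collection.
3. Correct Table 3 (T1 and T3 entries, item totals, footnote), step 14 (the fallback) and step 18 (the NEBH source) to match.
4. State where the range-of-motion and deformity points of HHS come from, and use the same source at T1 and T3.

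The cost is a survey revision, a small amendment and more burden on respondents. EQ-5D alone takes T3 from 34 to 34 + 6 = 40 items. The KOOS or hip items come on top, and the documents do not give their number. The 15-minute estimate would need revising, and a longer questionnaire may lower the response rate somewhat.

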For patient-reported outcomes (decision quality, quality of life, etc.), missing data items will be handled per established protocols for the validated surveys (e.g., missing knowledge items are considered incorrect). For item-specific analysis, our primary analyses will be conducted excluding patients with missing data. The treatment received (surgical vs non-surgical) will be assessed through chart review and confirmed via patient report (T3); therefore, is not subject to missing data. Even though we cannot test the missing at random assumption, we will first compare patients with and without missing data to gain insights. As a sensitivity analysis, we will conduct several missing imputation techniques: (1) last value carried forward (LVCF), (2) single imputation with EM algorithm and (3) multiple imputation. The LVCF approach applies to follow-up missing data, which is essentially the same as assuming no change over time. Compared with single imputation, the appealing aspect of the multiple imputation approach is incorporating the variability across imputation so that the statistical uncertainty due to missing is more properly accounted for. We will compare our findings from the primary analyses with the findings from different imputation strategies to determine whether our findings are stable across different assumptions. We will also report the uncertainty associated with the treatment effect as indicated in the SE estimates from the multiple imputation analysis.

As the first step, responders and non-responders will be compared across groups to examine non-response bias. For patient-reported outcomes, missing data will be handled per established protocols for the validated surveys. We will conduct sensitivity analyses to determine the impact of missing imputation.[3] The hypotheses will be evaluated using an intention-to-treat approach. The analysis plan for the primary outcome (hypothesis 1.1) will first calculate the rate of decision quality in each group, as the percentage of patients who meet or exceed the knowledge

threshold *and* receive treatment that matches their preference. A logistic regression model with the generalized estimating equations (GEE) approach will be used to compare the rates of decision quality of the DA-A and DA-B groups and account for the clustering of patients within providers.[4] Analysis will start by testing the interaction between the two intervention factors. It is plausible that an interaction between DAs and type of surgeon report exists for this analysis. Thus, the effective sample size will be limited to 117 per group when the comparisons are stratified by the type of surgeon report. The study has 89% power to detect a difference in the percentage of patients with high decision quality of 18%, from 65% in DA-B group to 83% in DA-A group.

For hypothesis 1.2, an interaction between DAs and PPR report is unlikely so there is no need to account for clustering within the same provider, thus, we will use a two-sample t-test to compare the mean knowledge score between the two groups. With approximately 560 patients from each group, we can invoke the Central Limit Theorem and use a two-sample t-test to compare mean knowledge score between the two groups, even if the knowledge score is not normally distributed. The study will have 80% power to detect a difference as small as 3.3% in total knowledge scores assuming the SD is 20%. For hypothesis 1.3, patient's treatment preference will be assessed before the surgeon visit so again, there is no need to account for clustering. A X² test will be used to compare the percentage of patients with clear treatment preference between the two groups. Hypothesis 2.1 will use a linear regression model with the GEE approach and hypothesis 2.2 will use logistic regression with GEE approach to account for clustering of patients within surgeons for these analyses.

The heterogeneity of the treatment effect will be explored by testing the interaction between interventions and different factors on study outcomes. These factors include (1) patient characteristics (e.g., age, gender, education level, joint (hip or knee), health literacy and severity of disease), (2) provider characteristics (gender, years since graduation, surgical volume), (3) intervention compliance (whether patients reviewed the DAs) and (4) mode of DA delivery (online or paper). Linear or logistic regression models (with the GEE approach in the case of clustering within providers) will be used to test the interaction between interventions and these factors. We will also report treatment effect in each subpopulation if there are strong evidence of

interactions between interventions and these factors. Some of the hypothesis testing here might be exploratory in nature. The study will have sufficient power for testing interaction for continuous outcomes (e.g., detecting meaningful ‘differences in differences’ for knowledge scores, EQ-5D scores) but not categorical outcomes (e.g., rate of high decision quality, surgical rate).

References

2. Bland M. *Cluster randomized trials in the medical literature. Notes for talks presented at University of York*: University of York, 2005.

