Osteoarthritis is a common and debilitating disease and a leading cause of disability in the U.S. and a growing public health problem. More than one-third of adults 65 and older have OA (1) and the majority report at least some degree of limitation. A significant percentage of patients with OA (40%) report that their overall health is only “fair” or “poor” (2). Studies have also found that adults with OA have higher rates of death from all causes, cardiovascular deaths, and dementia deaths (1.6, 1.7, and 2.0 times higher respectively) compared with the general population (3).

Joint replacement surgery is a common treatment for OA and more than 1,000,000 hip and knee replacements were performed in 2010 in the U.S (4). The decision about whether or not to have joint replacement surgery requires patients and clinicians to make tradeoffs between the chance of symptom relief and potential complications. For example, total hip or knee replacement provides a high likelihood of near complete pain relief (80-90%) but carries a small chance of serious complications (1-5%) and requires considerable time and effort for recovery (5,6). Delaying or waiting for surgery does not decrease the effectiveness, so in order to determine whether or when surgery may be warranted, providers need to understand how bothered patients are by their symptoms and how concerned they are about the prospect of having surgery. The decision to have surgery depends on a complex interplay of having an appropriate clinical condition and patients’ informed preferences.

Patients are not routinely informed or engaged in decisions about total joint replacement. Clinical guidelines for treatment of OA emphasize the importance of informing patients and engaging in shared decision making (SDM) to determine the best treatment (5,7). However, studies have found little evidence of shared decision making in routine care (8,9). Patients with hip and knee osteoarthritis are not well informed about the options and outcomes, and one third

report that they were never asked about their goals or treatment preferences for this elective procedure (8,9).

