Knee and Hip Osteoarthritis	
 • Diagnosis of knee or hip OA • Adults, age 21 or older • Scheduled new patient visit with participating orthopaedic specialist 	
 • Prior partial or total knee or hip replacement surgery on joint of concern within 5 years • Hip fracture or aseptic necrosis at any time in 12 months prior to visit • Rheumatoid arthritis or psoriatic arthritis • Does not read or write in English or Spanish • Unable to consent for self due to cognitive or other medical issue(s) • Prior decision aid order for joint of concern

Patient participants will be surveyed at three time points, before their visit with the surgeon, about one week after the visit, and again 12 months after the visit. Data from our previous studies suggests that we will have about 65 eligible new patients each month for the study enrollment period. We plan to enroll patients for about 12 months and estimate 1,120 patients will complete the first assessment in-clinic or before the visit with the surgeon, 840 (75%) will complete the second assessment one week after the visit, and 716 will complete the third assessment about one year after the visit. The sample size calculations consider both the potential for interaction effects between the interventions as well as the potential impact of clustering of patient participants within surgeons. Figure 2 offers a more detailed look at the projected screening and enrollment numbers.

Figure 2: CONSORT Flow diagram with estimates for screening, enrollment and response rates

Legend: PDA=patient decision aid, T1=in clinic before surgeon visit, PRO=patient reported outcomes; T2=1 week post visit; T3=6-12 month post visit

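### Two of the SAP's three missing-data sensitivity analyses are poor checks of stability for the T3 health outcomes, and none varies missing at random credibly

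*SAP*

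**What the plan says.** The missing-data paragraph of the SAP (unnumbered) sets out the following.

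- **Item level.** Missing items follow the scoring rules of each instrument. For item-specific analysis, "our primary analyses will be conducted excluding patients with missing data".
- **Sensitivity analyses.** There are three: LVCF for follow-up data, described as a method "which is essentially the same as assuming no change over time"; "single imputation with EM algorithm"; and multiple imputation. The SAP says multiple imputation reflects the uncertainty better than single imputation, and it takes the reported uncertainty of the treatment effect from the multiple-imputation standard errors.
- **Use.** Primary findings are compared with those from all the imputation strategies "to determine whether our findings are stable across different assumptions".
- **Missing at random.** The SAP concedes that this cannot be tested and plans a comparison of patients with and without missing data.
- **Surgery status.** It comes from chart review with patient confirmation and is treated as complete.

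On expected numbers, the Protocol (Research Design and Methods) has "estimate 1,120 patients will complete the first assessment in-clinic or before the visit with the surgeon", then "840 (75%) will complete the second assessment one week after the visit, and 716 will complete the third assessment about one year after the visit". Its Measures section schedules EQ-5D, KOOS and the Harris Hip Score at T1 and T3 only. Its Background says "total hip or knee replacement provides a high likelihood of near complete pain relief (80-90"%).

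**The concern.** A sensitivity analysis is useful if its assumption is a plausible alternative to the primary one. Two of the three planned here do not meet that test for T3 health outcomes.

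Under LVCF, a patient without a T3 health score keeps the T1 value, or a value returned with the T2 survey if the clinic one was missed (Study Procedures, item 11). For an operated patient that is in general a pre-operative score, whereas T3 is timed about six months after surgery (item 14). The Protocol's own account of what surgery does contradicts the assumption. Hypothesis 2.1 is most exposed, because it compares later health between patients of high and low decision quality, and hypothesis 2.2 expects those two groups to differ in surgical rate. The LVCF error may therefore differ between them.

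Single EM imputation has a different fault: filled-in values are counted as data, so standard errors come out too small. As normally run, it also shares the missing-at-random assumption of multiple imputation, so agreement between the two adds little.

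The assumption the SAP calls untestable is thus left without a credible challenge. LVCF is the only method that departs from it, and it does so in a direction the Background makes implausible. A finding could be called stable, or unstable, for reasons unrelated to how sensitive it is to the missing data.

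**Working it through.** **1. Projected non-completion (Protocol, Research Design and Methods).**
- T2: 840/1,120 = 75.0%, which matches the stated 75%. Missing: 280/1,120 = 25.0%.
- T3: 716/1,120 = 63.9%. Missing: 404/1,120 = 36.1%.

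These are survey figures among T1 completers.

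**2. LVCF.** Let D1 and D3 be the true group differences at T1 and T3, and m the fraction missing, equal in both groups and unrelated to outcome (assumed). LVCF then estimates (1 − m)·D3 + m·D1. If the groups differ only at follow-up (D1 = 0), it keeps 1 − m of the true difference:
- m = 0.25: 0.75
- m = 0.361: 0.64

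A simulation with 560 per group, a follow-up difference of 0.2 SD, T1-T3 correlation 0.3-0.7 and 2,000 runs per setting (all assumed) gave about 0.74 and 0.63-0.65. Hypothesis 2.1 compares non-randomised groups, so D1 may not be zero. LVCF then pulls the result towards the baseline difference.

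**3. Single imputation, data missing completely at random, no predictors, N = 1,120, n = 716.** The SAP does not say whether EM imputation adds residual noise, so both forms are shown.

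*Conditional mean.* The model SE is σ√(1 − m)/√N and the true SE is σ/√(N(1 − m)).
- Ratio = 1 − m = 0.64
- Coverage of a nominal 95% interval = 2Φ(1.96 × 0.639) − 1 = 79%

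*Noise added.* The model SE is σ/√N. The true variance is σ²/n + mσ²/N, because the noise also enters the estimate.
- Ratio = 1/√(1,120/716 + 0.361) = 1/√1.925 = 0.72
- Coverage = 2Φ(1.96 × 0.721) − 1 = 84%

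**4. If T1 predicts T3 (assumed correlation r = 0.3-0.7).** For an unadjusted mean with conditional-mean imputation, the ratio is √{[r² + (1 − r²)(1 − m)]/[r² + (1 − r²)/(1 − m)]}.
- r = 0.3: √(0.672/1.513) = 0.67
- r = 0.7: √(0.816/1.288) = 0.80

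The understatement is then smaller. In a group comparison that itself adjusts for T1, the simulation gave 0.63-0.64 across the same correlations, so the relief is confined to unadjusted comparisons.

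**The case against.** Much can be said for the plan, and several stronger readings fail.

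- **That robustness rests on LVCF and single imputation alone.** It does not. Multiple imputation is the third method, the SAP rates it above single imputation, and the reported standard errors come from it. The ratios in steps 3 and 4 do not apply to those.
- **That both weak methods assume no change.** Only LVCF does, and the SAP says so openly.
- **That the primary result is biased by these methods.** They are sensitivity analyses and leave the primary estimate untouched.
- **That the SAP plainly makes complete cases primary with 25-36% missing throughout.** The exclusion sentence is limited to item-specific analysis. Complete-case primary handling of unreturned surveys is a fair inference, but the available text does not spell it out. Nor does the range apply everywhere: the SAP plans hypothesis 1.2 on about 560 per group, hypothesis 1.3 uses pre-visit preference, and surgery, the outcome of hypothesis 2.2, is treated as complete.
- **That 36% of EQ-5D or KOOS values will be missing.** The Protocol's Table 3 marks these measures as routinely collected at T3, and Study Procedures item 18 draws on the MGH and NWH registries. These may fill gaps at two of the three sites.
- **That noise-added imputation gives a ratio of √(1 − m) = 0.80 and 88% coverage.** This leaves out the variance the noise adds to the estimate.

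It is also fair that carrying knowledge forward from before the visit to one week after is far less implausible than carrying a pain score past surgery. What stands is narrower: for T3 health outcomes, two of the three checks are weak, the available text does not specify the imputation model, and no analysis credibly varies missing at random.

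**Conclusion.** The point holds for the sensitivity analyses of T3 health outcomes, chiefly under hypothesis 2.1. LVCF conflicts with the Protocol's own expectation after surgery and, at 36% missing, keeps about 64% of a difference that arises only at follow-up. Single EM imputation, in the no-predictor illustration, shows 0.64-0.72 of the true standard error and 79-84% coverage, with less understatement in unadjusted comparisons when T1 predicts T3.

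These sizes assume data missing completely at random, equal missingness in the groups, and survey non-completion standing in for missing health scores. If the registries recover scores, m falls and both effects shrink. They measure how badly the checks could mislead a judgement of stability and are not estimates of bias in the trial's primary result. The change is worth making before analysis, because the better method is already in the plan.

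**What to change.** For T3 health outcomes:

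1. Drop LVCF and single EM imputation, and name multiple imputation as the lead sensitivity analysis.
2. Specify the imputation model: arm, site, surgeon clustering, joint, age, T1 knowledge, treatment preference, T1 EQ-5D and KOOS or Harris Hip Score, and chart-confirmed surgery status.
3. Add delta-adjusted (tipping-point) multiple imputation: shift the imputed scores over a pre-stated range, separately by group, and report the shift at which the conclusion changes. The Protocol's minimally important change of 0.1 for EQ-5D is one available anchor.
4. State how unreturned T2 and T3 surveys are handled in the primary analysis, and whether registry scores replace a missing T3 survey score.

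The cost is SAP wording, modest extra programming and the need to agree a delta range; no new data are needed. Whether multiple imputation should become the primary analysis is a debatable trade-off and is left to the sponsor.
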